8.3.4. Electrocardiograms

Single 12-lead ECGs will be obtained as outlined in the SoA (see [Table 3](#) and [Table 4](#)) using an ECG machine that automatically calculates the heart rate and measures PR, QRS, QT, and QTcF intervals; if necessary, calculation of such parameters is also acceptable if the ECG machine does not perform it automatically. All 12-lead ECGs will be performed with the participant in a recumbent or semirecumbent position after 5 minutes of rest. Prolonged QTcF values of ≥ 450 milliseconds are to be confirmed by performing 2 additional ECGs (within the next 5 minutes) and averaging the results to determine the averaged value.

Additional 12-lead ECGs may be performed at other visits as deemed clinically necessary. Electrocardiograms will be interpreted by the investigator at the site or designee, and the results will be used for immediate management of the participant's care. The decision to include or exclude a participant or withdraw a participant from the study based on an ECG flagged as "Abnormal, Clinically Significant" is the responsibility of the investigator, in consultation with the sponsor's medical monitor, as appropriate. Any abnormalities that are considered clinically significant in the judgment of the investigator are to be reported as AEs. ECGs should be performed in line with local standards and results reported in the eCRF.

8.3.5. Laboratory Assessments

See [Table 13](#) for the list of clinical laboratory tests to be performed and [Table 3](#) and [Table 4](#) for the laboratory assessment visit schedule. A central laboratory will perform all clinical laboratory assessments for safety (ie, blood chemistries, hematology assessments, coagulation tests, endocrine function, and urinalysis), [REDACTED]. [REDACTED]

[REDACTED] Additional testing may be required by the investigator or sponsor based on emerging safety data. All Protocol-required laboratory assessments must be conducted in accordance with the Laboratory Manual and [Table 3](#) and [Table 4](#).

If visits at Week 2, Week 6, Week 26, and Week 30 are scheduled as remote, blood collection will be conducted remotely (eg, participant's home or workplace); otherwise blood will be collected during in-clinic visit (see [Table 3](#) and [Table 4](#)). At-home sampling for additional laboratory assessments may also be conducted; see [Appendix E](#) for COVID-19-related guidance.

Information regarding collection, processing, and shipping of samples for laboratory assessment is provided in the Laboratory Manual.

Clinically significant abnormal laboratory findings are those that are not associated with the underlying disease, unless judged by the investigator to be more severe than expected for the participant's condition. All laboratory tests with values considered clinically significantly abnormal during participation in the study (including any unscheduled testing within the 24-week follow-up period) should be repeated until the values return to normal or baseline or are no longer considered clinically significant by the investigator or medical monitor.

If screening laboratory assessments are performed more than 32 days before Day 1, then the tests must be repeated and eligibility confirmed before study drug administration on Day 1.

Laboratory sample collection on Day 1 must be performed before study drug administration.

See Section 9.1 for information regarding laboratory abnormalities that should be recorded as an AE in the eCRF.

Table 13: Required Laboratory Analytes

Blood Chemistries	Hematology	Urinalysis	Serology / Infection	Pregnancy Testing

 • Albumin • Alkaline phosphatase • ALT • AST • Bicarbonate or CO₂ • Blood urea nitrogen or urea • Calcium • Chloride • Creatine kinase • Creatinine • Glucose • GGT • Lactate dehydrogenase • Phosphate • Potassium • Sodium • Total bilirubin • Direct bilirubin (if total bilirubin is elevated above 1.5 × ULN) • Total protein 	
Complete blood count, including:
 
 • Hemoglobin • Mean corpuscular volume • Hematocrit • Platelet count • Mean platelet volume • In samples with abnormalities in platelet count or size distribution (as indicated by an automated analyzer), a blood film should be examined. • Red blood cell count • Red blood cell distribution width (RDW) • WBC count 
Differential count (% and absolute values), including:
 
 • Basophils • Eosinophils • Lymphocytes • Monocytes • Neutrophils 	
 • Color and appearance • pH and specific gravity • Bilirubin • Glucose • Ketones • Leukocyte esterase • Nitrite • Occult blood • Protein • Microscopic evaluation (in case of abnormal urinalysis results) 	
 • HBsAg* • HBsAb • HBcAb* • HCVAb* • HIV • QuantiFERON-TB Gold test 
*Observation: If either HBsAg or HBcAb is positive, a reflexive HBV DNA must be obtained. If HCVAb is positive, a reflexive HCV RNA must be obtained.
	
Pregnancy testing will be performed only for female participants. Further instructions are provided in Section 8.3.5.1.
 
 • Serum FSH: for confirmation of nonchildbearing status for WONCBP (screening only) • Serum pregnancy test (WONCBP): to be performed at visits indicated in Table 3 and Table 4. • Urine pregnancy test (WONCBP): to be performed at visits indicated in Table 3 and Table 4. 
Pregnancy tests (serum or urine) should be repeated if required by local regulations.

		Lipid Panel	Coagulation	Thyroid Function Markers
		
 • Total cholesterol • Triglycerides • LDL • HDL 
Observation: Fasting is not required.
	
 • PT • INR 	
 • TSH • Free T₄ 
Inflammation Marker
 
 • hsCRP

Note: Additional tests may be required, as agreed upon by the investigator and sponsor, based on emerging safety data or to rule out a diagnosis.

Note: Alternative tests (ie, CO₂ or CO₂ Combining Power or HCO₃) are also allowed as per regional standard of care.

8.3.5.1. Pregnancy Testing

A serum FSH test will be required for all WONCBP during screening (before the first dose of study drug) for confirmation of nonchildbearing status. Women of nonchildbearing potential are defined as surgically sterile with a hysterectomy and/or bilateral oophorectomy OR postmenopausal, defined as amenorrhea \geq 12 months prior to screening.

A serum pregnancy test will be required for all WOCBP during screening (before the first dose of study drug) and at the visits indicated in [Table 3](#) and [Table 4](#). Urine pregnancy tests will be performed locally as outlined in [Table 3](#) and [Table 4](#), as medically indicated (eg, in case of loss of menstrual cycle, when pregnancy is suspected), or per country-specific requirement (note that country-required urine pregnancy testing will be outlined and communicated to investigational sites under separate cover). If a urine pregnancy test is positive, the results should be confirmed with a serum pregnancy test.

If the serum pregnancy test is negative after a urine test was positive, the investigator will assess the potential benefit/risk to the participant and determine whether it is in the participant's best interest to resume study drug and continue participation in the study.

If a pregnancy is confirmed by a serum pregnancy test, the participant should be immediately discontinued (see Section [7.1](#)). Additionally, Section [9.7](#) should be followed for reporting requirements.

8.3.5.2. Serology

Hepatitis B and C and HIV screening assessments will be performed at the screening visit to rule out infection; required analytes are shown in [Table 13](#). Generally, hepatitis and HIV tests should be performed early in the screening process due to the length of time needed to obtain the results. Additional tests may be performed if clinically indicated.

Eligibility criteria for participants with a history of HCV infection should generally require participants to have completed curative antiviral treatment and require HCV viral quantitative RNA below the limit of quantification 12 weeks after the end of HCV therapy. A patient who is HCVAb positive but HCV RNA negative due to prior treatment or natural resolution should be eligible.

Reactivation of HBV can occur in chronic carriers of HBV infection (HBsAg-positive, undetectable or low HBV DNA, and normal ALT) who are not on HBV therapy or in individuals who have serologic evidence of a resolved prior HBV infection (ie, HBsAg-negative and anti-HBc-positive). While HBsAg-negative, anti-HBc-positive patients are at lower risk of HBV reactivation compared with HBsAg-positive patients, risk of HBV reactivation should be considered in all participants.

Participants with no prior history of HBV infection who have been vaccinated against HBV and who have a positive antibody against HBV surface antigen as the only evidence of prior exposure may participate in the study.

8.3.5.3. Tuberculosis Screening

At the time of screening, all participants will undergo TB screening. Depending on the TB status of the participant, different assessments may be performed.

The QFT-GIT is the preferred testing method. If the QFT-GIT cannot be performed, or if the results cannot be determined by the reference laboratory to be either positive or negative (eg, indeterminate), then participants may be screened using the PPD tuberculin skin test (Mantoux method; see Note 1) with approval of the medical monitor (or designee). The QFT-GIT is an indirect test for *Mycobacterium tuberculosis* infection (including disease) and is intended for use in conjunction with risk assessment, radiography (see Note 2), and other medical and diagnostic evaluations.

[figure not shown]
It is recommended that participants with a history of Bacille Calmette-Guérin vaccination be tested with the QFT-GIT, because the Mantoux/PPD tuberculin skin test may be positive due to vaccination.

A QFT-GIT or Mantoux/PPD tuberculin skin test is not required if the participant has previously received a documented adequate course of therapy for either latent TB infection (eg, 9 months of isoniazid in a locale where rates of primary multidrug TB resistance are < 5% or an acceptable alternative regimen) or active TB infection (an acceptable multidrug regimen). In such cases, a chest x-ray(s) or other appropriate diagnostic image, performed within 3 months of Day 1, is required (see Note 2). To be considered eligible for the study, the x-ray(s) must be negative for active TB infection as determined by a qualified radiologist (see Note 2). Documentation of adequate treatment for TB and negative chest x-ray(s) results must be obtained prior to Day 1.

Note 1: If the QFT-GIT cannot be performed, or if the results cannot be determined to be positive or negative (eg, indeterminate), then participants may be screened using the PPD tuberculin test (Mantoux method), with the approval of the medical monitor (or designee).

Participants must have the PPD test administered and evaluated by a health care professional 48 to 72 hours later in order to be eligible for the study, unless performed and documented within the past 3 months. The test should be performed according to local standards with induration of < 5 mm required for inclusion.

Note 2: At the discretion of the investigator or medical monitor (or designee), participants may be required to have a chest x-ray (posterior-anterior and lateral views) or other appropriate diagnostic image (ie, computed tomography or magnetic resonance imaging) taken at screening, or previously taken within 3 months prior to Study Day 1, and read by a qualified radiologist to potentially distinguish between latent and active TB. Documentation of adequate treatment for TB and negative chest x-ray(s) results must be obtained prior to Day 1.

8.6. Unscheduled Visits

Unscheduled visits may occur at any time at the investigator's (or designee's) discretion and appropriate clinical and laboratory tests may be performed as clinically indicated.

If there is a potential clinically significant abnormality in hematology or chemistry assessments (particularly in platelet count) during the study, an unscheduled visit within the following week should occur to repeat laboratory assessments (further details are provided in [Table 9](#) and [Table 10](#)). The investigator must inform and consult the sponsor (or designee) regarding any hematologic abnormality.

8.7. End of Treatment and/or Early Termination

When the participant permanently discontinues study drug, whether the participant is terminating the study early or the participant has completed the study, the EOT visit should be conducted. If the EOT visit coincides with a regular study visit, the EOT evaluations will supersede those of that scheduled visit, and the data should be entered in the EOT visit in the eCRF. The participant should be encouraged to return for the follow-up visits (EOS, [REDACTED]).

8.8. Follow-Up

Adverse events and SAEs must be reported up until at least 28 (+ 7) days after the last dose of study drug [REDACTED], and ongoing AEs and SAEs must be followed up until toxicities resolve, return to baseline, or are deemed irreversible, whichever is longer. Reasonable efforts should be made to have the participant return for the follow-up visit and report any AEs that may

occur during this period. In exceptional cases when the participant cannot return to the site for the safety follow-up visit, the participant should be contacted by telephone for assessment of AEs and SAEs and the site should properly document the contact.

8.8.1. Safety Follow-Up

The safety follow-up period is the interval between the EOT visit and the scheduled follow-up visit (EOS), which should occur 28 (+ 7 days) after the EOT visit (or after the last dose of study drug if the EOT visit was not performed).

[REDACTED]

[REDACTED]

[REDACTED]

[REDACTED]

9. ADVERSE EVENTS: DEFINITIONS AND PROCEDURES FOR RECORDING, EVALUATING, FOLLOW-UP, AND REPORTING

9.1. Definition of Adverse Event

Adverse Event Definition

• An AE is any untoward medical occurrence associated with the use of a drug in humans, whether or not it is considered drug-related.• An AE can therefore be any unfavorable or unintended sign (including an abnormal laboratory finding), symptom, or disease (new or exacerbated) temporally associated with the use of study drug.
Additional Guidance for Events Meeting the Adverse Event Definition

• Any safety assessments (eg, ECG, vital signs measurements), including those that worsen from baseline, considered clinically significant in the medical and scientific judgment of the investigator (ie, not related to progression of underlying disease) are to be reported as an AE.• Abnormal laboratory test results are to be reported as an AE if they are considered clinically meaningful, induce clinical signs or symptoms, require concomitant therapy, or require changes in study drug. Whenever possible, a diagnosis (eg, anemia, thrombocytopenia) should be recorded in the eCRF rather than the abnormal laboratory test result (eg, low hemoglobin, platelet count decreased).• Exacerbation of a chronic or intermittent pre-existing condition/disease, including either an increase in the frequency and/or intensity of the condition, is to be reported as an AE.• New conditions detected or diagnosed after the start of study drug administration are to be reported as an AE.• Signs, symptoms, or the clinical sequelae of a suspected drug-drug interaction are to be reported as an AE.• Signs and/or symptoms from dosing errors of a study drug (eg, overdose) or a concomitant medication are to be reported as an AE.• "Lack of efficacy," "disease progression," or "failure of expected pharmacological action" will not be reported as an AE or SAE. Such instances will be captured in the efficacy assessments.• A condition that leads to a medical or surgical procedure (eg, endoscopy, appendectomy) will be reported as an AE if it occurs after obtaining informed consent. If the condition is present before entering the study, then it should be captured as medical history.• Pre-existing diseases or conditions with expected fluctuations in signs or symptoms should be reported as an AE only if the investigator judges the fluctuation to have worsened more than expected during study participation.

9.2. Definition of Serious Adverse Event

If an event is not an AE per the definition above, then it cannot be an SAE even if serious conditions are met (eg, hospitalization for signs/symptoms of the disease under study, death due to progression of disease).

A serious adverse event is defined as any untoward medical occurrence that, at any dose:	
a. Results in death	
b. Is life-threatening	
The term "life-threatening" in the definition of "serious" refers to an adverse drug experience that places the participant, in the opinion of the initial reporter, at immediate risk of death from the adverse experience as it occurs. This does not include an adverse drug experience that, had it occurred in a more severe form, might have caused death.

c. Requires inpatient hospitalization or prolongation of existing hospitalization	
In general, hospitalization signifies that the participant has been detained (involving at least an overnight stay) at the hospital or emergency ward for observation and/or treatment that would not have been appropriate in the physician's office or outpatient setting. Complications that occur during hospitalization are AEs. If a complication prolongs hospitalization or fulfills any other serious criteria, the event is serious. When in doubt as to whether hospitalization occurred or was necessary, the AE should be considered serious.
 
Hospitalization for elective treatment or planned surgery (eg, stent replacement, hip surgery) is not considered an SAE.
 
Hospitalization for medical interventions in which no unfavorable medical occurrence occurred (ie, elective procedures or routine medical visits) is not considered an SAE.

d. Results in persistent or significant disability/incapacity	
The term "disability" means a substantial disruption of a person's ability to conduct normal life functions. This definition is not intended to include experiences of relatively minor medical significance, such as uncomplicated headache, nausea, vomiting, diarrhea, influenza, and accidental trauma (eg, sprained ankle), that may interfere with or prevent everyday life functions but do not constitute a substantial disruption.
e. Is a congenital anomaly/birth defect	
f. Is an important medical event	
An important medical event is an event that may not result in death, be immediately life-threatening, or require hospitalization but may be considered serious when, based on appropriate medical judgment, the event may jeopardize the participant and may require medical or surgical intervention to prevent one of the outcomes listed in the above definition. Examples of such events include new invasive or malignant cancers, intensive treatment in an emergency department or at home for allergic bronchospasm, blood dyscrasias, or convulsions that do not result in hospitalization, development of drug dependency or drug abuse, or suspected transmission of an infectious agent via a medicinal product. Secondary malignancies should always be considered SAEs.

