8.2.2. Adverse Event Summaries

Adverse events will be summarized by treatment group and overall INCB054707 dose groups for the safety population in the PC period. For the extension evaluable population in the extension

period and for participants who took INCB054707 45 mg or 75 mg throughout study participation, AEs will be summarized by treatment group and overall.

An overall summary of AEs will include the following:

- Number (%) of participants reporting any TEAEs
- Number (%) of participants reporting any serious TEAEs
- Number (%) of participants reporting any Grade 3 or higher TEAEs
- Number (%) of participants reporting any treatment-related TEAEs
- Number (%) of participants who temporarily interrupted study treatment because of TEAEs
- Number (%) of participants who permanently discontinued study treatment because of TEAEs
- Number (%) of participants who had a fatal TEAE

The following summaries will be produced by MedDRA term (if 10 or fewer participants appear in a table, a listing may be appropriate):

- Summary of TEAEs by MedDRA SOC and PT
- Summary of TEAEs by MedDRA PT in decreasing order of frequency
- Summary of TEAEs by MedDRA SOC, PT, and maximum severity
- Summary of TEAEs by MedDRA SOC, PT, and CTCAE grade category
- Summary of Grade 3 or higher TEAEs by MedDRA SOC and PT
- Summary of Grade 3 or higher TEAEs by MedDRA PT in decreasing order of frequency
- Summary of serious TEAEs by MedDRA SOC and PT
- Summary of serious TEAEs by MedDRA PT in decreasing order of frequency
- Summary of treatment-related TEAEs by MedDRA SOC and PT
- Summary of treatment-related TEAEs by MedDRA PT in decreasing order of frequency
- Summary of Grade 3 or higher treatment-related TEAEs by MedDRA SOC and PT
- Summary of treatment-related serious TEAEs by MedDRA SOC and PT
- Summary of TEAEs with a fatal outcome by MedDRA SOC and PT
- Summary of TEAEs leading to dose interruption by MedDRA SOC and PT
- Summary of TEAEs leading to discontinuation of study drug by MedDRA SOC and PT
- Summary of TEAEs requiring concomitant medications by MedDRA SOC and PT

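### The elective-admission exemption in Protocol 9.2(c) is not limited to conditions present at consent, so a new or worsened AE can lose SAE status when a scheduled admission is the only seriousness criterion it meets

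*Protocol*

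**What the plan says.** Protocol Section 9.2 lists inpatient hospitalization, or its prolongation, as seriousness criterion c. Two exemptions follow in the same cell. The first concerns elective or planned admissions: "Hospitalization for elective treatment or planned surgery (eg, stent replacement, hip surgery) is not considered an SAE". It carries no condition on when the underlying problem arose or when the admission was booked. The second comes straight after it and is tied to the absence of an untoward event: "Hospitalization for medical interventions in which no unfavorable medical occurrence occurred (ie, elective procedures or routine medical visits) is not considered an SAE".

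Section 9.1 sorts conditions that lead to a procedure by timing. Such a condition "will be reported as an AE if it occurs after obtaining informed consent". A condition that was already there at entry is handled differently: "If the condition is present before entering the study, then it should be captured as medical history". The same section makes exacerbations and newly diagnosed conditions AEs. For pre-existing conditions with expected fluctuations, it asks for worsening beyond what was expected.

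Section 9.2 opens with the rule that something that is not an AE cannot be an SAE. Section 9.3 tells the investigator to judge seriousness by Section 9.2, and Section 9.4 requires SAEs to be reported within 24 hours. SAP 8.2.2 tabulates, by treatment group, "Number (%) of participants reporting any serious TEAEs".

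**The concern.** The exemption turns on how an admission was arranged. Elsewhere the AE and SAE sections turn on whether the condition began or worsened after consent. Two participants with the same new condition could be classified differently because one was admitted urgently and the other was given a date.

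Two outputs depend on that classification: the 24-hour SAE report to the sponsor, and the serious TEAE tables by dose group. Treatment runs for up to 52 weeks in adults up to age 75, which leaves time for a new condition to be diagnosed and booked for inpatient care. Sections 9.5 and 9.5.1 define no events of clinical or special interest, so that route does not offer a second way to capture such an event.

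**Working it through.** **Step 1. What the first exemption does that other rules do not.** The question is which admissions would change status if the sentence were deleted.

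| Situation | Status without the sentence | Status with the sentence |
|---|---|---|
| Condition present at consent, not an AE under 9.1; scheduled admission | Medical history, so not an SAE (9.1 and the opening of 9.2) | Same |
| Admission with no untoward event | Not an SAE (second exemption) | Same |
| AE that began or worsened after consent; unscheduled inpatient admission | Serious under c | Same |
| AE that began or worsened after consent; scheduled inpatient admission | Serious under c | Not serious under c; serious only through a, b, d, e or f |

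Only the fourth row changes. The sentence may have been meant as a clarification of the first two rows, but its independent effect falls largely on new or worsened conditions.

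**Step 2. Whether another provision restores seriousness in the fourth row.**

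- Doubt rule: "When in doubt as to whether hospitalization occurred or was necessary, the AE should be considered serious". It covers doubt about whether an admission happened or was needed, and does not address doubt about whether it was elective.
- Complication rule: "If a complication prolongs hospitalization or fulfills any other serious criteria, the event is serious". It covers what happens during the stay, and does not reach the condition that led to it.
- Criterion f: an event "may be considered serious when, based on appropriate medical judgment, the event may jeopardize the participant and may require medical or surgical intervention". This route is open and needs no hospitalization, but it is permissive and depends on judgment.
- Criteria a, b, d and e, and the rule that secondary malignancies are always SAEs, apply unchanged.

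The gap is therefore confined to AEs for which hospitalization is the only criterion met and the investigator does not invoke criterion f.

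**Step 3. Size.** The plan gives no figure to reproduce. SAP 3.1 gives about 40 participants per group; assume that all are dosed.

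- One participant in one arm: 1/40 = 2.5 percentage points.
- One participant in the pooled active groups, which SAP 8.2.2 also summarizes for the placebo-controlled period: 3 × 40 = 120, and 1/120 = 0.8 percentage points.
- Exact (Clopper-Pearson) 95% upper limits: 0/40 gives 1 − 0.025^(1/40) = 8.8%; 1/40 gives 13.2%; 2/40 gives 16.9%.

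The counts 0, 1 and 2 are assumed, to show the scale. They are not forecasts, because the documents give no rate of elective or scheduled admissions.

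**The case against.** The strongest reply is that the sentence closes only one route to seriousness. It sits under criterion c and speaks of hospitalization; the other criteria stand beside it. A new condition that needs intervention may well qualify under criterion f. This is right. A reader might infer that any serious condition arising on study drug is counted as non-serious once its admission is scheduled. The documents do not support that.

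A second reply is that context suggests a narrower meaning. The second exemption links elective procedures to the absence of an untoward event, replacing a stent presupposes an existing one, and planned surgery can be read as surgery planned before entry. Sections 9.1 and 9.2 also do different jobs, AE status and seriousness, so they do not contradict each other outright. That reading is possible, but the text does not state it, and Step 1 shows that it would leave the sentence almost nothing to do. An investigator who follows the words may exempt a new condition.

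A third reply concerns consequences, and most of it stands. The event is still recorded as an AE and enters the TEAE tables. Where applicable, it also enters those for Grade 3 or higher, interruption, discontinuation and concomitant medication. For events that CTCAE does not classify, the fallback Grade 3 definition in Section 9.3 mentions hospitalization. The argument from time on drug is weakest for the placebo comparison, which ends at Week 24. The SAE completion guide and Study Reference Manual, which are not available here, may clarify the exemption.

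**Conclusion.** The point holds in a limited form. As written, 9.2(c) lets an AE that begins or worsens after consent lose SAE status when it leads to a scheduled inpatient admission and meets no other criterion. Such an event could miss the 24-hour report and the serious TEAE counts, but it would not disappear from the safety data.

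A reader might go further and conclude that drug-attributable serious events will be under-counted. The documents support only that they could be: the number affected cannot be estimated and may be zero. Each such participant is 2.5 percentage points of an arm's serious TEAE rate, given about 40 dosed per arm.

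The conclusion assumes that investigators apply the sentence literally and that no site guide narrows it. It is worth correcting because the rule can produce a wrong classification and the remedy is short.

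**What to change.** In 9.2(c), limit the first exemption to admissions for conditions that were present at informed consent and have not become AEs under Section 9.1, meaning not new and not worsened more than expected. Apply the same limit to the elective-procedures wording in the second exemption. Then add a sentence on these lines:

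*An AE under Section 9.1 that requires inpatient hospitalization is serious under criterion c, whether or not the admission was scheduled.*

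Tying the limit to Section 9.1 matters. Withdrawing the exemption for any worsening would set a lower threshold than 9.1 uses for fluctuating pre-existing conditions, and would sit badly with the rule that a non-AE cannot be an SAE.

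The cost is a small edit to 9.2, a matching check of the SAE completion guide, a slightly higher SAE count and a few more 24-hour reports. No new data collection or change to the SAP tables is needed.
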